**Model Checking & Diagnostics**

- Posterior density plots and plots of the posterior samples (chains) will be produced for all the parameters in the model.
- The posterior density for the adjusted mean change from baseline in E-RS: COPD total score in each treatment group and differences versus placebo for each danirixin dose will be plotted.
- The Gelman-Rubin R estimate from the three chains will be calculated for all parameters in the model and the differences from placebo for each danirixin dose.

**Model Results Presentation**

The following will be presented for each analysis based on the best fitting model using all post-burn in samples available.

- The posterior mean, median, SD and 90% credible interval (CrI) for the change from baseline in E-RS: COPD total score for each treatment group.
- The posterior mean and 90% CrI for the difference from placebo for each danirixin dose.

- The posterior probability that difference from placebo is less than 0, -0.5, -1, -1.5 and -2 for each danirixin dose.
- For the strategic interim, the posterior predictive probability of success for each danirixin dose, where success is the probability that the difference from placebo is less than 0 is >95%.
- A figure of the fitted mean dose response model with the 90% CrI for all possible doses in the dose range, overlaid with the Month 6 adjusted posterior means and 90% CrI from the longitudinal model in Section 7.1.3.

### Sensitivity and Supportive Analyses

- At the strategic interim, a supportive analysis will be conducted to estimate the effect of actual treatment in the population of participants who were confirmed as having CMH according to SGRQ, were symptomatic at baseline, did not experience a protocol deviation considered to impact efficacy, and completed six months of treatment. The population used will be the Symptomatic population; all other details will be the same as for the primary analysis.

#### 7.1.2. E-RS: COPD Subscale Scores Dose-Response Analysis

The primary analysis described in Section 7.1.1 will be repeated for the three E-RS: COPD subscale scores of breathlessness, cough and sputum and chest symptoms.

#### 7.1.3. E-RS: COPD Total and Subscale Scores Longitudinal Analysis

The estimand is the effect of actual treatment in the population of participants who did not experience a protocol deviation considered to impact efficacy. A supportive analysis will be performed to assess the effect of randomized treatment in all randomized and dosed participants.

A Bayesian mixed effects analysis with repeated measures (MMRM) will be performed on the monthly E-RS: COPD total and subscale scores.

A frequentist MMRM analysis will be performed on the monthly E-RS: COPD total scores and repeated to assess the impact of various covariates.

##### 7.1.3.1. Endpoint

Change from baseline in monthly mean E-RS: COPD total and subscale scores as defined in Section 14.6.3.

##### 7.1.3.2. Summary Measure

For the Bayesian MMRM the summary measure is the adjusted posterior mean difference from placebo for each danirixin dose.

For the frequentist MMRM the summary measure is the adjusted mean difference from placebo for each danirixin dose.

##### 7.1.3.3. Population of Interest

PP population.

**7.1.3.4. Strategy for Intercurrent (Post-Randomization) Events**

A ‘hypothetical’ strategy will be used to account for the intercurrent events of occurrence of a protocol deviation considered to impact efficacy during the treatment period (see [Appendix 1](#)) and treatment discontinuation, to estimate the effect if participants had not deviated from the protocol and remained on treatment. Only E-RS: COPD data prior to the occurrence of a protocol deviation considered to impact efficacy or treatment discontinuation will be used in the analysis. Subsequent data up to Month 6 will be assumed to be missing at random (MAR).

**7.1.3.5. Statistical Analyses / Methods**

**7.1.3.5.1. Bayesian MMRM Methodology Specification**

Endpoint / Variables

 
Change from baseline in monthly E-RS: COPD total and subscale scores
 

Model Specification

 
Bayesian mixed models repeated measures approach.
 
The model will include treatment*visit, baseline*visit, country and smoking status parameters. Note that the model will not include an intercept. Visit will consist of six levels (Month 1-Month 6), and Treatment will consist of six levels (placebo and 5 active doses). If the model does not run, the country covariate will be removed.
 
The priors for the mean vector for each of the parameters (i.e covariates) will each follow a normal distribution with mean 0 and SD 1000. The prior for the variance-covariance will follow an inverse Wishart distribution with degrees of freedom equal to the number of visits and an identity scale array. 150,000 samples will be generated with a thin of 75 after a burn-in of 10,000 samples. The number of samples or thin may be increased as needed to reduce the MCSE/SD<0.01 as deemed necessary.
 
Three chains will be used to calculate the gelman-rubin R statistic:             
 
Chain 1: The starting value for all covariates in the model will be 0.
 
Chain 2: The starting value for all covariates in the model will be 2.
 
Chain 3: The starting value for all covariates in the model will be -2.
 
 
 
The seeds used to for the three chains were generated using the ranuni function in SAS and are listed in Section 14.5.2.
 
All post-burn-in samples will be used when creating outputs.
 

Model Checking & Diagnostics

 
Posterior density plots and plots of the posterior samples (chains) will be produced for all the parameters in the model.
 
The posterior density for the adjusted mean change from baseline in E-RS: COPD score in each treatment group and differences versus placebo for each danirixin dose will be plotted.
 
The Gelman-Rubin R estimate from the three chains will be calculated for all parameters in the model and the differences from placebo for each danirixin dose.
 
Distributional assumptions underlying the model used for analyses using MMRM will be examined by obtaining a normal probability plot of the residuals and a plot of the residuals versus the fitted values (i.e. checking the normality assumption and constant variance assumption of the model respectively) to gain confidence that the model assumptions are
 

reasonable. Plots of residuals versus covariates and baseline versus response will also be examined.

Model Results Presentation
 
 
• The adjusted posterior mean change from baseline and the associated 90% equi-tailed CrI for each Month for each treatment.
 
• The adjusted mean difference from placebo and the associated 90% equi-tailed CrI for each Month for each danirixin dose.
 
• The probability that each treatment difference is less than 0, -0.5, -1, -1.5 and -2 for each month for each danirixin dose.
 
• A figure of the posterior mean and 90% equi-tail CrI for each Month for each treatment.
 


Sensitivity and Supportive Analyses
 
 
• At the strategic interim a supportive analysis of monthly E-RS: COPD total score will be conducted to estimate the effect of actual treatment in the population of participants who were confirmed as having CMH according to SGRQ, were symptomatic at baseline, and did not experience a protocol deviation considered to impact efficacy. The population used will be the Symptomatic population; all other details will be the same as for the primary analysis.
 
• At the strategic interim a further supportive analysis will be conducted to estimate the effect of the randomized treatment. The population used will be the ITT (according to randomized treatment). A 'treatment policy' strategy will be used to account for the intercurrent event of occurrence of a protocol deviation considered to impact efficacy during the treatment period (see Appendix 1). All E-RS: COPD data up the time of treatment discontinuation or Month 6 (see Section 14.6.3) will be used in the analysis, regardless of any protocol deviation. A 'hypothetical' strategy will be used to account for the intercurrent event of treatment discontinuation. Data after treatment discontinuation will be considered MAR.
 

**7.1.3.5.2. Frequentist MMRM Methodology Specification**

Endpoint / Variables
 
 
• Change from baseline in monthly E-RS: COPD total score
 

Model Specification
 
 
• The following covariates will be included in the model: baseline, country, smoking status at screening, treatment, Month, Month*baseline and Month*treatment interactions, where Month is nominal. Month will consist of six levels (Month 1-Month 6), and treatment will consist of six levels (placebo and 5 active doses)
 
• Two models will be fitted; one with a response variable of E-RS: COPD Total Score, and one with a response variable of change from baseline in E-RS: COPD Total Score.
 
• An unstructured covariance structure for the R matrix will be used by specifying 'type=UN' on the REPEATED line.
 
• The Kenward and Roger method for approximating the denominator degrees of freedom and correcting for bias in the estimated variance-covariance of the fixed effects will be used. If this method does not run, the residual method will be used instead
 
• The OM option will be used to derive the least square (LS) means using coefficients which are based on the participants used in the analysis. The OM option requires an OM dataset which has a row for every participant-visit combination that contains all of the covariates used in the model and a macro variable containing the mean baseline for the participants used in the
 

analysis.
Model Checking & Diagnostics

 
Distributional assumptions underlying the model used for analyses using MMRM will be examined by obtaining a normal probability plot of the residuals and a plot of the residuals versus the fitted values (i.e. checking the normality assumption and constant variance assumption of the model respectively) to gain confidence that the model assumptions are reasonable. Plots of residuals versus covariates and baseline versus response will also be examined.
 

Model Results Presentation

 
LS mean and LS mean changes from baseline with their corresponding standard errors (SEs) for each Month and each treatment
 
Estimated treatment differences from placebo and corresponding 90% confidence intervals (CIs) and p-values for each Month and each danirixin dose.
 
A figure of LS mean changes from baseline and 90% CIs for each treatment by Month will be generated.
 
A figure of LS mean and 90% CIs for each treatment by Month will be generated.
 
The type III tests of fixed effects from the model will be presented.
 

Summary Results Presentation

 
A figure of daily mean E-RS: COPD total and subscale scores over time (Days -7 to 168) for the PP population.
 
A figure of daily mean E-RS: COPD total and subscale scores over time by completer status (Days -7 to 168) for the PP population.
 
A figure of daily mean change from baseline E-RS: COPD total and subscale scores over time for the PP population.
 
A figure of daily mean (<math>\pm</math> SE) change from baseline E-RS: COPD total and subscale scores over time for each dose and placebo in a separate panel. This figure will be produced for the PP and Symptomatic populations (Strategic interim only).
 
A figure of daily mean (<math>\pm</math> SE) E-RS: COPD total and subscale scores over time (Days -7 to 168) for each dose and placebo in a separate panel. This figure will be produced for the PP population.
 
Summary statistics for baseline E-RS: COPD total and subscale scores for each treatment and overall for participants with non-missing score for each Month, for the PP and Symptomatic (Strategic interim only) population.
 
Summary statistics for raw and change from baseline monthly mean E-RS: COPD total and subscale scores for each month for each treatment, for the PP and Symptomatic population (Strategic interim only).
 
Empirical distribution function plot of E-RS: COPD Total Scores at Baseline and at Month 6.
 

## 7.2. Secondary Efficacy Analyses

The estimand is the effect of actual treatment in the population of participants who did not experience a protocol deviation considered to impact efficacy.

A supportive analysis will be conducted to estimate the treatment policy effect of the randomized treatment on the annual rate of HCRU exacerbations in all randomized and dosed participants.

**7.2.1. Annual Rate of HCRU Exacerbations and Annual Rate of EXACT Events**

**7.2.1.1. Endpoint**

Annual rate of moderate/severe HCRU exacerbations as defined in Section 14.6.3.

Annual rate of EXACT events as defined in Section 14.6.3.

**7.2.1.2. Summary Measure**

Rate ratio (also expressed as percentage rate reduction) for each danirixin dose vs. placebo

**7.2.1.3. Population of Interest**

PP population

**7.2.1.4. Strategy for Intercurrent (Post-Randomization) Events**

The intercurrent events of interest are occurrence of a protocol deviation considered to impact efficacy during the treatment period (see Appendix 1) and treatment discontinuation. An ‘as treated’ strategy will be used to account for these events to estimate the effect if participants had not deviated from the protocol and remained on treatment. Only HCRU exacerbations/EXACT events prior to the occurrence of a protocol deviation considered to impact efficacy will be used in the analysis.

**7.2.1.5. Statistical Analyses / Methods**

**7.2.1.5.1. Statistical Methodology Specification**

Endpoint / Variables

 
• Annual rate of On-treatment moderate/severe HCRU exacerbations
 
• Annual rate of On-treatment EXACT events
 

Model Specification

 
• Bayesian generalized linear model assuming a negative binomial distribution for the underlying exacerbation rate with a log link function
 
• Terms in the model:             
 
○ Response: number of on-treatment, moderate/severe HCRU exacerbations or EXACT events per participant.
 
○ Categorical: treatment group, gender, exacerbation history (<math>\leq 1</math>, <math>\geq 2</math> moderate/severe), smoking status (screening), country
 
○ Continuous: post-bronchodilator % predicted FEV1 (Screening)
 
○ An offset to account for the length of time on treatment for each participant will be
 
 
 

- included in the model as  $\log_e$  (length of time) as defined in Section 14.6.3.
- Non-informative priors will be used for all modelling parameters. Wherever possible conjugate priors will be utilised.
- All the terms in the model will follow a normal distribution with a mean of 0 and a SD of 100, except for dispersion which follows a gamma distribution with shape and inverse scale of 0.001.
- Three chains will be used to calculate the gelman-rubin R statistic:
  - Chain 1: The starting value for all covariates in the model will be the maximum likelihood estimation (MLE), except dispersion which will be 0.1.
  - Chain 2: The starting value for all covariates in the model will be 130% of the MLE, except for dispersion which will be 0.2.
  - Chain 3: The starting value for all covariates in the model will be 70% of the MLE, except for dispersion which will be 0.4.
- The seeds used to for the three chains were generated using the ranuni function in SAS and are listed in Section 14.5.2.
- Burn-in 2000, thin 5, and 10,000 MCMC samples will be generated for 2000 retained samples

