10.5.1.2. Key Secondary Analyses

All analyses for other efficacy endpoints will use the mITT Population, unless otherwise noted. Dose will be treated as a categorical variable and no dose response modelling will be done unless otherwise stated. The treatment comparisons of interest will be between individual danirixin doses and placebo and between different danirixin doses. Smoking status (current vs former) will be included as a covariate in all analyses. All Bayesian analyses will use non-informative priors. Further details will be described in the RAP.

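### The dispersion prior in the exacerbation-rate model is not non-informative: if dispersion means k, it can hold moderately overdispersed data near Poisson and make the 90% intervals up to about 6% too narrow

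*SAP*

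**What the plan says.** SAP 7.2.1.5.1 covers the annual rate of moderate/severe HCRU exacerbations and the annual rate of EXACT events. The model is a "Bayesian generalized linear model assuming a negative binomial distribution for the underlying exacerbation rate with a log link function".

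- **Priors.** The section states that "Non-informative priors will be used for all modelling parameters". Protocol 10.5.1.2 says the same of the secondary analyses: "All Bayesian analyses will use non-informative priors". The regression terms get normal priors with mean 0 and SD 100, "except for dispersion which follows a gamma distribution with shape and inverse scale of 0.001". The SAP does not say how dispersion enters the variance.
- **Chains.** The three chains start dispersion at 0.1, 0.2 and 0.4 ("The starting value for all covariates in the model will be the maximum likelihood estimation (MLE), except dispersion which will be 0.1", and likewise for the other two). The run length is "Burn-in 2000, thin 5, and 10,000 MCMC samples will be generated for 2000 retained samples".
- **Diagnostics.** The plan asks for Gelman-Rubin statistics for every parameter and for the rate ratios, residual Q-Q plots with simulated envelopes, and autocorrelation plots.
- **Reporting.** For each dose the outputs are the median rate ratio with a 90% credible interval and the probabilities that the true ratio is below 1, 0.9 and 0.8.
- **Sensitivity.** The only supportive analysis listed is an ITT repeat at the strategic interim. No alternative prior is planned.

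**The concern.** A gamma density with shape 0.001 rises like 1/k towards zero. That does no harm when the likelihood vanishes at zero. Here it does not vanish: as k goes to 0 the negative binomial likelihood tends to the Poisson likelihood, which is positive. The prior spike can therefore survive into the posterior and pull the fit towards a model without overdispersion, although the negative binomial was chosen to allow for it.

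The HCRU exacerbation rate is a key secondary endpoint in the protocol synopsis. If the fit is held near Poisson while the data are overdispersed, the rate-ratio intervals are too narrow and the reported probabilities lean slightly towards overconfidence. All three chains start k between 0.1 and 0.4, none near zero and none well above 0.4. Agreement between them is therefore a limited check on whether the spike has been explored.

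**Working it through.** The documents state no prior mass, event rate, dispersion or power for this endpoint, so there is no figure of the plan's own to reproduce.

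**1. Prior mass.** For small x, the Gamma(0.001, rate 0.001) distribution function is approximately (0.001·x)^0.001 / Γ(1.001), with Γ(1.001) ≈ 0.9994.

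- P(k < 1e-10) ≈ exp(0.001 × ln 1e-13) / 0.9994 = 0.9705 / 0.9994 = 0.971.
- P(k < 0.01) ≈ exp(0.001 × ln 1e-5) / 0.9994 = 0.9886 / 0.9994 = 0.989.
- P(0.1 < k < 3) ≈ 0.001 × ln 30 = 0.0034.

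**2. Evidence needed to leave zero.** Near the estimate of k the prior density is about 0.001/k, and the spike near zero has mass close to 1. Treating the likelihood peak as normal with standard error se, the posterior odds of negative binomial to Poisson are about 0.001 × √(2π) × (se/k) × exp(ΔlogL), with √(2π) = 2.507. For se/k = 0.4 the odds are even when ΔlogL = ln(1/0.00100) = 6.9, a likelihood-ratio statistic of 13.8. For se/k of 0.25 to 0.6 the statistic is 14.7 to 13.0.

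**3. What narrowing is possible.** A completer's time at risk is 168 + 3 = 171 days (SAP 14.6.3, offset), or 0.468 year. At 1.0 per year the mean count is 0.468. The Poisson standard error relative to the negative binomial one is 1/√(1 + k·mu): 0.918 at k = 0.4 and 0.825 at k = 1.0. Full collapse would matter most at large k, so the question is whether it happens there.

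**4. Simulation.** From the documents: six equal arms (protocol 10.3), about 540 completers and hence 540/6 = 90 per arm (protocol 5.2), and 0.468 year at risk. Assumed: the annual rates and k, the k parameterisation, no covariates and no true treatment effect. The posterior of k was integrated on a grid, and Exp(1) on k served as a benchmark prior. The median likelihood-ratio statistic (LR) and width ratio come from 500 trials per cell. The mean posterior mass and coverage come from 1,500 trials × 5 comparisons per cell.

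| Rate/yr | k | Median LR | Mean posterior mass, k < 0.01 | Width, SAP/benchmark | 90% coverage, SAP prior | 90% coverage, Exp(1) |
|---|---|---|---|---|---|---|
| 0.8 | 0.4 | 3.7 | 0.88 | 0.944 | 88.7% | 90.8% |
| 0.8 | 0.7 | 11.0 | 0.54 | 0.952 | 88.5% | 90.4% |
| 0.8 | 1.0 | 20.8 | 0.20 | 0.979 | 89.5% | 90.2% |
| 1.0 | 0.4 | 6.2 | 0.80 | 0.941 | 87.8% | 90.0% |
| 1.0 | 0.7 | 17.0 | 0.30 | 0.969 | 89.3% | 90.3% |
| 1.0 | 1.0 | 31.7 | 0.05 | 0.994 | 89.2% | 89.5% |
| 1.5 | 0.4 | 13.9 | 0.42 | 0.958 | 87.7% | 89.5% |
| 1.5 | 0.7 | 37.7 | 0.03 | 0.995 | 90.2% | 90.4% |
| 1.5 | 1.0 | 68.8 | 0.00 | 1.000 | 90.4% | 90.4% |

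The pattern follows step 2. Where the typical LR is well below 14 the posterior sits mostly at Poisson; where it is well above 14 the data override the prior.

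**5. Other runs.** With half-normal(SD 2) as comparator, 2,000 trials per setting at rates of 0.8 to 1.3 and k of 0.4 to 0.6 gave coverage of about 88% under the SAP prior. P(RR < 1) exceeded 0.95 in 5.4% to 6.2% of null comparisons, against 4.4% to 5.0% with the half-normal. A further 600 trials per setting gave 87% to 89% for k of 0.4 to 0.7 at 0.8 to 1.0 per year, and 87% at 1.5 per year with k = 0.4.

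**The case against.** **The prior mass alone proves nothing about the posterior.** A reader might infer from the 97% below 1e-10 that the model becomes Poisson whatever the data show. The documents do not support that: they give neither rate nor dispersion, and with about 540 completers the data dominate once overdispersion is large. This stands and limits the point.

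**The effect is small.** The loss is about two points of coverage, and the benchmark priors sometimes cover slightly above 90%, so part of the width gap belongs to them. The SAP has no success threshold for exacerbations; the 0.95 used above comes from its strategic-interim criterion for E-RS:COPD. This stands too. A shortfall against the nominal 90% remains in the affected cells.

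**The simulation is not the SAP's sampler.** In an indicative check with two simple Metropolis samplers at the SAP's chain length and starting values (12 trials per cell), the chains visited the spike only part of the time. Intervals were about 1% to 4% narrower than with half-normal(2). That lowers the likely harm, but it also means the reported interval could depend on how often a finite chain reaches zero.

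**The diagnostics are broader than Gelman-Rubin.** The Q-Q envelopes and autocorrelation plots could show unmodelled overdispersion or chains sticking near zero. True, but none of them compares priors.

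**Dispersion is undefined.** If it means the inverse (size) parameter, mass near zero implies extreme overdispersion and the argument reverses. The starting values would then correspond to k of 10, 5 and 2.5, which makes the k reading more plausible without settling it.

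**The model has already been run unblinded at the strategic interim.** A change of prior now affects comparability. Keeping the present prior as a sensitivity run answers this, and the SAP's amendment table already records changes to another Bayesian model to improve convergence and mixing.

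**Conclusion.** The point holds in conditional form. The label non-informative is wrong for this prior if dispersion is k. The prior can then hold the model near Poisson unless the likelihood-ratio statistic for overdispersion reaches about 14. Under assumed annual rates of 0.8 to 1.5 and k of about 0.4 to 0.7, intervals are up to about 6% too narrow, coverage is about 87% to 89%, and P(RR < 1) is slightly overconfident. Within that range the effect has already gone at 1.5 per year with k = 0.7, and it is negligible at 1 per year with k about 1.

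Two further inferences are not supported. One is that the probabilities are materially overconfident for every dose: that depends on the unstated rate and dispersion. The other is that the EXACT analysis suffers equally: no EXACT rate was simulated, and a higher event rate would weaken the prior's pull. The primary E-RS:COPD analysis does not use this model. This is a modest calibration fault in a secondary analysis, worth correcting because the correction is cheap.

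**What to change.** In SAP 7.2.1.5.1, for the final analysis:

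1. State the parameterisation, for example that dispersion is k in variance = mu + k·mu².
2. Replace the dispersion prior with a weakly informative one without a pole at zero, for example half-normal(0, SD 2) or Exp(1) on k.
3. Keep the gamma(0.001, 0.001) prior as a named sensitivity run, for comparability with the strategic interim.
4. Spread the chain starting values for k to include one near zero and one well above 0.4, for example 0.01, 0.5 and 2.
5. Check the rate ratios and interval widths against the maximum-likelihood negative binomial fit, which is already needed for the chain starting values.

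The cost is a few lines of SAP text, one extra run and slightly wider intervals.
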